1.0 Introduction

This Statistical Analysis Plan (SAP) describes the statistical analyses for elezanumab (ABT-555) Study M19-148: A Randomized, Double-Blind, Placebo-Controlled Proof-of-Concept Study to Assess the Safety and Efficacy of Elezanumab in Acute Ischemic Stroke.

The analyses of pharmacokinetic and pharmacodynamic fluid biomarkers will not be covered in this SAP.

This is the second version of the SAP. If applicable, the SAP will be updated to include changes to analyses implemented in protocol amendments and/or analyses that are different from the latest version of the protocol. Details will be outlined in Section [13.0](#). The SAP will not be updated in case of administrative changes or amendments to the protocol unless the changes impact the analysis.

Unless noted otherwise, all analyses will be performed using SAS Version 9.4 (SAS Institute Inc., Cary, NC 27513) or later.

2.0 Study Design and Objectives

2.1 Objectives and Hypotheses

The objective is to assess the efficacy, safety, tolerability, and pharmacokinetics (PK) of elezanumab in subjects with acute ischemic stroke.

This study will assess the proof-of-concept of the use of elezanumab in the improvement of neurologic function in patients with acute ischemic stroke.

2.2 Study Design Overview

[figure not shown]
This is a 52-week, Phase 2a, randomized, double-blind, parallel-group, placebo-controlled, multicenter proof-of concept study to evaluate the safety and efficacy of elezanumab in subjects with acute ischemic stroke.

Administration of blinded study drug must be initiated as soon as possible but no later than 6 hours after randomization and done every 4 weeks thereafter through Week 48 for a total of 13 doses. The final double-blind Treatment Period study visit will be at Week 52. Subjects will have 2 post-treatment follow-up visits at 12 and 24 weeks after last dose of study drug, and a final follow-up phone call 39 weeks (~5 half-lives) after last dose of study drug.

Final efficacy analyses will be performed after the last subject completes the Week 52 visit and after an interim database lock. Final safety analyses will be performed following completion of the post-treatment period and final database lock.

The schematic of the study is shown in [Figure 1](#).

Figure 1. Study Schematic

EVT endovascular therapy; hr(s) hour(s); IV intravenous; LKN last known normal; tPA tissue plasminogen activator; Wk week

2.3 Treatment Assignment and Blinding

Subjects will be randomized to elezanumab or placebo in a 1:1 ratio. Randomization will be stratified by intravenous (IV) tissue plasminogen activator (tPA) use (yes/no), treatment with endovascular therapy (EVT) (yes/no), and by time since "last known normal" (\leq 11 hours or $>$ 11) at the time of randomization.

The primary analysis of efficacy endpoints will be performed after the last subject completes the Week 52/Premature discontinuation visit. At this time, an interim database lock will occur, the randomization will be loaded into the database and the Data and Statistical Sciences department at AbbVie will perform the statistical analysis. Final safety analyses and post-treatment efficacy analyses will be performed following completion of the post-treatment period and database lock.

Study sites and subjects will remain blinded through the duration of the study.

2.4 Sample Size Determination

The primary efficacy endpoint is the monthly-adjusted, model-based area under the curve (AUC) of the National Institutes of Health Stroke Scale (NIHSS) total score during the Treatment Period. Approximately █ subjects will be randomized to elezanumab █ mg or placebo in a █ ratio. Assuming the true difference in AUC is █, this sample size is sufficient to show a █ difference in AUC (with the elezanumab group having a lower, i.e., better, AUC) between treatment and placebo with a posterior probability of > █%. This sample size was calculated based on simulations and included a █% mortality rate for the population under █ years of age, █% mortality rate for the population greater than or equal to █ years of age, and an additional █% discontinuation rate.

The number and proportion of missing assessments (due to missed visits or study drug discontinuation) will be monitored on an ongoing basis and if the proportion of missing assessments is higher than planned, additional subjects may be randomized.

3.0 Endpoints

3.1 Primary Endpoint

The primary endpoint is the NIHSS total score during the Treatment Period. The primary analysis will be a comparison of a model-based AUC of the NIHSS total score between elezanumab and placebo.

3.2 Secondary Endpoint

The secondary endpoint is the proportion of subjects with a favorable outcome based on the modified Rankin Scale (mRS) at Week 52. A favorable outcome is defined as having an mRS score of 0, 1, or 2 at the specified time point.

**3.4 Safety Endpoints**

Safety evaluations include adverse event (AE) monitoring, serious adverse event (SAE) monitoring, adverse events of special interest (AESI) monitoring, physical examinations, neurologic examinations, vital sign measurements, clinically significant magnetic resonance imaging (MRI) abnormalities, electrocardiogram (ECG) variables, Columbia-Suicide Severity Rating Scale (C-SSRS) assessments, and clinical laboratory testing (hematology, chemistry, and urinalysis) as measures of safety and tolerability for the entire study duration.

[figure not shown]
3.5 Other Endpoints

Brain MRI scans will be obtained for all subjects at Baseline (collected between 2-4 days after randomization) and follow-ups (Week 4 and Week 52). Images will be analyzed to assess infarct (ischemic core and penumbra) and presence of microstructural damage related to myelin loss and axonal destruction.

4.0 Analysis Sets

The following population sets will be used for the analyses.

The Full Analysis Set (FAS) includes all randomized subjects who receive any study drug. Subjects will be grouped according to treatment as randomized. The FAS will be used for all efficacy, demographic, and baseline analyses.

The Safety Analysis Set consists of all subjects who receive any study drug. Subjects will be included in the analysis according to the study drug that they actually receive regardless of the randomized treatment assigned as defined below.

If a subject was randomized to treatment X, but received treatment Y during the entire study, this subject will be included in the Y treatment group for analysis purposes. If a subject receives both treatments but one > 50% of the time, the subject will be included in that treatment group. If a subject receives both treatments an equal percentage of the time, the subject will be analyzed in the treatment group to which they were randomized.

5.0 Subject Disposition

The total number of subjects who were screened (Overall only), enrolled (randomized), and treated will be summarized.

A summary of subject accountability overall and by country/investigator will be provided where the number of subjects in each of the following categories will be summarized for each treatment group and overall:

- Subjects randomized in the study
- Subjects who took any study drug (Safety Analysis Set)
- Subjects who completed study drug
- Subjects who prematurely discontinued study drug
- Subjects who completed the study
- Subjects who prematurely discontinued study
- Subjects in each efficacy analysis set (FAS, MMIAS)

For end of study participation, the number and percentage of subjects who completed study drug and the study and those who prematurely discontinue with associated reasons will be summarized overall and by treatment group.

6.0 Study Drug Duration and Compliance

For the Safety Analysis Set, extent of exposure will be summarized for each treatment group. Extent of exposure will be summarized as duration of treatment and number of infusions. Duration of treatment is defined for each subject as last dose date minus first dose date + 28. A gap in treatment due to missed infusions will not be considered in the calculation of study drug duration. Duration of treatment will be summarized using the number of subjects treated, mean, standard deviation, median, minimum and maximum. In addition, the number and percentage of subjects in each unique treatment duration interval (28, 29 to 56, 57 to 84, 85 to 112, 113 to 140, 141 to 168, 169 to 196, 197 to 224, 225 to 252, 253 to 280, 281 to 308, 309 to 336, 337 to 364, > 364) will be summarized.

The number and percentage of subjects who received each number of infusions from 1 to 13 will be summarized.

Because the treatment is administered by the site, compliance will not be summarized.

7.0 Demographics, Baseline Characteristics, Medical History, and Prior/Concomitant Medications

Demographics, baseline or disease characteristics, medical history, and prior and concomitant medications will be summarized for the FAS by treatment group and overall. Categorical variables will be summarized with the number and percentage of subjects; percentages will be calculated based on the number of non-missing observations. Continuous variables will be summarized with descriptive statistics (number of non-missing observations, mean and standard deviation, median, minimum and maximum).

7.1 Demographics and Baseline Characteristics

Continuous demographic variables include age, weight (by sex and overall), height, and body mass index (BMI). Categorical demographic variables include sex, ethnicity, race, age (< 70, 70 - < 80, ≥ 80), weight (< 60 or ≥ 60 kg), BMI (< 25 or ≥ 25 kg/m²), country (United States, Non-US), nicotine user (current, former, never, unknown for each type), and alcohol user (current, former, never, unknown).

7.2 Medical History

Medical history data will be coded using the Medical Dictionary for Regulatory Activities (MedDRA). The actual version of the MedDRA coding dictionary will be noted in the statistical tables and clinical study report. The number and percentage of subjects in each medical history category (by MedDRA system organ class (SOC) and preferred term) will be summarized overall and by treatment group for the FAS. The SOC will be presented in alphabetical order, and the preferred terms will be presented in alphabetical order within each SOC. Subjects reporting more than one condition/diagnosis will be counted only once in each row (SOC or preferred term).

The following stratification factors related to the current stroke will be summarized with the number and percentage of subjects in each category:

- Time since last known normal (\leq 12 hours between last known normal and study drug initiation, $>$ 12 hours between last known normal and study drug initiation) based on the stroke history eCRF. Randomization is stratified by time from last known normal to randomization transaction (\leq 11 hours or $>$ 11 hours) for operational purposes. Time from last known normal to study drug initiation will be used for analysis purposes.
- Treatment with tPA (Yes, No) based on the prior and concomitant medications and supplements eCRF.
- Treatment with EVT (Yes, No) based on the prior and concomitant procedures eCRF.
- Treatment with EVT and/or tPA (Yes, No) based on the eCRFs noted above. Yes indicates treatment with either or both EVT and tPA, and No indicates treatment with neither.

Additionally, the number and percentage of subjects with baseline NIHSS total score categories of $<$ 15, and \geq 15, and the number and percentage of subjects with reperfusion as measured by the modified Thrombolysis in Cerebral Infarction (mTICI)² score ($<$ 2B, \geq 2B) as reported by the central reader will be summarized by treatment group. Baseline NIHSS total score will also be summarized continuously.

Time between last known normal and study drug initiation will be summarized both as a continuous variable and a categorical variable (0 - 6 hours, $>$ 6 - 12 hours, $>$ 12 - 18 hours, $>$ 18 - 24 hours, $>$ 24 hours).

Discharge destination, time from last known normal to discharge post-stroke in days, and stroke subtype based on the Stroke History eCRF will be summarized.

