4 INVESTIGATIONAL PLAN

4.1 Overall Study Design and Plan

This is a 52-week, Phase 2a, randomized, double-blind, parallel-group, placebo-controlled, multicenter proof-of concept study to evaluate the safety and efficacy of elezanumab in subjects with acute ischemic stroke.

The schematic of the study is shown in [Figure 1](#). Further details regarding study procedures are located in the Operations Manual ([Appendix F](#)). Also see Section 5 for information regarding eligibility criteria.

The Screening Period is up to 24 hours since "last known normal" (the time before hospital arrival at which the subject was last known to be without the signs and symptoms of the current stroke or at his or her baseline state of health). Treatment with IV tPA and/or EVT will be allowed before randomization and will be recorded as a concomitant therapy.

[figure not shown]
Randomization will be stratified by IV tPA use (yes/no), by EVT use (yes/no), and by time since last known normal (≤ 11 hours or > 11 hours). The proportion of subjects enrolled who have EVT is targeted to be up to approximately 50% of the study population. A target of approximately 25% to 50% of subjects may be randomized within the time window of ≤ 11 hours since last known normal. Lastly, the proportion of subjects who enroll > 80 to 90 years of age is targeted to be up to approximately 30% of the study population. Eligible subjects will be randomized in a 1:1 ratio to receive either elezanumab 1800 mg or placebo as an IV infusion.

Administration of blinded study drug must be initiated as soon as possible but no later than 6 hours after randomization and done every 4 weeks thereafter through Week 48 for a total of 13 doses. The final double-blind Treatment Period study visit will be at Week 52. Subjects will have 2 post-treatment follow-up visits at 12 and 24 weeks after last dose of study drug, and a final follow-up phone call 39 weeks (5 half-lives) after last dose of study drug. All follow-up visits beginning at Week 4 during the Treatment Period and Follow-up Period will be allowed a window of \pm 7 days, and study procedures may be conducted over a period of 2 days. Unblinded safety data will be reviewed by an external DMC per the DMC Charter.

Final efficacy analyses will be performed after the last subject completes the Week 52 visit. Final safety analyses will be performed following completion of the post-treatment period and database lock.

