5.4 Prior and Concomitant Therapy

Use of IV tPA and/or EVT as part of acute care for the index stroke before or after randomization is permitted and must be recorded in the electronic case report form (eCRF). Eligibility according to NIHSS score must be confirmed at least 1 hour after completion of IV tPA and/or EVT (after completion of all treatments) and once any confounding effects of sedation or anesthesia have resolved before a subject can be randomized. All other standard-of-care treatments for the management of acute ischemic stroke and associated complications/comorbidities are permitted at the investigator's discretion.

Any medication or vaccine (including over-the-counter or prescription medicines, vitamins, and/or herbal supplements) that the subject received within 30 days before enrollment or is administered during the study must be recorded through the post-treatment visits (39 weeks after last dose of study drug). Given the acute nature of the Screening Period, medical history and information on prior therapy may be collected and/or confirmed at subsequent visits. All concomitant medications, including any change in dose must be recorded with the reason for use, dates of administration, dosages and frequency in the eCRF.

Rehabilitation is an integral part of post-stroke therapy. For subjects who receive rehabilitation therapy, the type (e.g., physical, occupational, speech), setting, and duration of rehabilitation will be recorded throughout the study as concomitant therapy using a structured patient- or caregiver-reported questionnaire.

Sites are encouraged to raise any questions regarding concomitant or prior therapy to the AbbVie emergency contact, if needed. Information regarding potential drug interactions with elezanumab is located in the elezanumab IB.²

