7.3 Prior and Concomitant Medications

The number and percentage of subjects taking prior and concomitant medications will be summarized separately by generic name based on the World Health Organization (WHO) Drug Dictionary. A prior medication is defined as any medication taken prior to the date of the study drug initiation. A concomitant medication is defined as any medication that started prior to the date of study drug initiation and continued to be taken after study drug initiation or any medication that started on or after the date of study drug initiation, but not after the date of the last dose of study drug plus 39 weeks (273 days).

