8.0 Efficacy Analyses

8.1 General Considerations

All efficacy analyses will be conducted in the FAS. Where noted, some analyses may additionally be conducted in the MMIAS. Because this is a small, exploratory, proof of concept study, p-values will not be presented. Where statistical models are noted, appropriate point estimates and 95% confidence intervals will be presented.

The primary analysis of efficacy endpoints will be performed after all ongoing subjects have completed the Treatment Period and an interim lock has been performed. This will be the final analysis for the efficacy endpoints during the Treatment Period.

Post treatment efficacy analyses will be completed following the final database lock.

Generally, "Baseline" refers to the last non-missing observation before the first administration of study drug. Where noted, Day 2-4 or Week 4 may be used as baseline. Unless otherwise specified, categorical variables will be summarized with the number and percentage of subjects in each category. Responder analyses will be presented with the number and percentage of subjects in each category, the difference in proportion of responders between the 2 treatment groups, and the 95% confidence interval for the difference based on Wald confidence limits, unless otherwise specified. Continuous variables will be analyzed using Mixed-Effect Model for Repeat Measures (MMRM) method. The dependent variable will be the visit value and baseline (pre-dose, Day 2-4 or Week 4, depending on the endpoint) will be included as one of the timepoints in the repeated measures. For analyses of change from baseline (pre-dose, Day 2-4 or Week 4, depending on the endpoint), this will be derived from a contrast of the group-level least squares (LS) means from the MMRM.

Unless otherwise specified, any subject who is randomized based on a wrong stratum will be analyzed according to the actual stratum the subject belongs to based on the eCRFs as noted in Section [7.2](#).

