8.3.3 Primary Efficacy Analysis

The primary efficacy analysis will be based on the monthly-adjusted area under the curve (AUC) derived from an MMRM. The dependent variable is the NIHSS total score during the Treatment Period. The model will include the stratification factors of tPA use (Y/N), EVT use (Y/N), time since last known normal (≤ 12 hours, > 12 hours based on time between last known normal and study drug initiation), main effects of treatment group and visit, and the treatment-by-visit interaction. The REPEATED statement will be used for visit with blocks in the covariance matrix identified by subject nested within treatment group. The unstructured covariance structure will be used to estimate the within subject variance-covariance; if the model does not converge with this variance-covariance structure, then compound symmetry will be used.

The monthly-adjusted AUC of NIHSS total score for each treatment group will be obtained using the trapezoidal method where i = treatment group (placebo, elezanumab) and j = visit during the Treatment Period {Day 1, Day 2-4, Week 4, Week 8, Week 12, Week 24, Week 36, Week 52}:

$$AUC_i = \frac{1}{13} \sum_{j=Stabil.(Day 2-4)}^{Week 52} \frac{(Week Number_j - Week Number_{j-1})}{4} \frac{1}{2} (LS Mean_{i,j} + LS Mean_{i,j-1})$$

The AUC for each treatment group, as well as the difference in AUCs (placebo minus elezanumab) and their respective standard errors and confidence intervals will be presented.

The posterior probability that the difference in AUCs being greater than 0.6 based on the observed data will be presented.

The attributes of the estimand corresponding to the primary efficacy objective are summarized in [Table 1](#).

Table 1. Summary of the Estimand Attributes Corresponding to the Primary Efficacy Objective

Estimand Label	Attributes of the Estimand					Statistical Summary
	Treatment	Endpoint	Population	Handling of Intercurrent Events		
NIHSS total score AUC	Elezanumab 1800 mg or placebo IV Q4W (13 doses)	NIHSS total score at each visit	FAS	Missing data due to intercurrent events (e.g., premature discontinuation of study drug, lost to follow-up, death, COVID-19) will be handled using MMRM with MAR assumption	Difference in monthly-adjusted AUC between treatment groups	

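### The SAP sets the tPA and EVT covariates from forms with no time cut-off, so treatment given after randomisation can be counted as a baseline stratum

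*SAP*

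**What the plan says.** **How the covariates are derived.** SAP 7.2 lists the stratification factors related to the current stroke and names a data source for each: "Treatment with tPA (Yes, No) based on the prior and concomitant medications and supplements eCRF" and "Treatment with EVT (Yes, No) based on the prior and concomitant procedures eCRF". Neither entry gives a time limit. The third factor, time since last known normal, does have a stated anchor (study drug initiation), and SAP 7.2 explains why it differs from the 11-hour randomisation stratum.

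**Where they are used.** SAP 8.3.3, on the primary MMRM: "The model will include the stratification factors of tPA use (Y/N), EVT use (Y/N), time since last known normal". The GLMMs in SAP 8.2 and 8.4 carry the same two terms. SAP 8.6 defines subgroups by tPA, by EVT and by either.

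**When treatment may be given.** Protocol 4.1, like the synopsis, says: "Treatment with IV tPA and/or EVT will be allowed before randomization and will be recorded as a concomitant therapy". Protocol 5.4 goes further: "Use of IV tPA and/or EVT as part of acute care for the index stroke before or after randomization is permitted", and requires the use to be entered in the eCRF.

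**What the SAP says about strata.** SAP 8.1 states that a subject randomised in a wrong stratum "will be analyzed according to the actual stratum the subject belongs to based on the eCRFs", pointing back to 7.2. SAP 8.2, in its general description of the MMRM, refers to the main stratification factors as at randomisation, unless noted otherwise.

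**The concern.** A stratification covariate should be fixed before treatment is assigned. As SAP 7.2 is written, tPA and EVT status can be changed by something that happens afterwards. Later reperfusion treatment may follow early worsening or a newly found occlusion (a clinical inference; the documents do not say so), in which case it would be related to outcome.

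Two things are at stake. The analysed strata may no longer match the randomised strata, and the tPA/EVT subgroups may be partly defined by later events. If later use also differs by arm, the primary AUC difference is adjusted for a consequence of treatment. The examples of intercurrent events in SAP Table 1 do not include later tPA or EVT, so this covariate is the only place where the plan would absorb it.

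**Working it through.** **Step 1: follow one subject through the text.** Take a subject correctly randomised as EVT = No who then has EVT for the index stroke.

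- Protocol 5.4 permits this and requires it to be recorded.
- The procedures form named in SAP 7.2 then holds an EVT entry.
- SAP 7.2 sets EVT to Yes or No from that form, so the literal result is Yes.
- SAP 8.1 does not settle the case. The subject was not in a wrong stratum at randomisation, yet a comparison of IRT with eCRF would show a mismatch, and no rule separates an entry error from later treatment.
- SAP 8.2 points to No, but only as a general description.

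**Step 2: can the form label separate early from late treatment?** No. Protocol 4.1 records even treatment before randomisation as concomitant. SAP 7.3, which covers medications only, counts as concomitant "any medication that started on or after the date of study drug initiation". That rule works by date, so tPA given before randomisation on the day of the first infusion also falls there. Only timing relative to randomisation can separate the two.

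**Step 3: how many subjects?** The documents give no rate. If 2% to 10% of 120 subjects were treated later (assumption), that is 0.02 × 120 = 2.4 to 0.10 × 120 = 12. This is an upper limit on those reclassified, since a subject already Yes on that factor does not move.

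**Step 4: how large could the shift be?** The plan has no figure to reproduce; the sample-size inputs in protocol 7.7 and SAP 2.4 are redacted. In a linear model with the AUC difference taken as placebo minus elezanumab, replacing the pre-randomisation covariate by the any-time covariate moves the estimate by

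shift = γ × (p_E − p_P),

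where γ is the coefficient of the any-time covariate and p_E, p_P are the proportions classed Yes in the elezanumab and placebo arms. If later use is equal across arms, the shift is zero whatever γ is.

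A large-sample simulation (400,000 subjects) used these assumptions: 50% with EVT before randomisation (the protocol's target ceiling), EVT coefficient −1, AUC SD 5, assumed effect 1.2, and later users 3 or 6 NIHSS points worse. Later use is expressed as a share of subjects without earlier EVT.

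| Later use, placebo / elezanumab | Later users worse by | Pre-randomisation covariate | Any-time covariate | Shift |
|---|---|---|---|---|
| 10% / 10% | 3 | 1.18 | 1.18 | 0.00 |
| 10% / 10% | 6 | 1.21 | 1.21 | 0.00 |
| 20% / 20% | 3 | 1.22 | 1.22 | 0.00 |
| 20% / 20% | 6 | 1.21 | 1.21 | 0.00 |
| 10% / 5% | 3 | 1.29 | 1.31 | 0.02 |
| 10% / 5% | 6 | 1.39 | 1.40 | 0.01 |
| 20% / 10% | 3 | 1.34 | 1.37 | 0.03 |
| 20% / 10% | 6 | 1.52 | 1.52 | 0.00 |
| 20% / 0% | 3 | 1.49 | 1.56 | 0.07 |
| 20% / 0% | 6 | 1.81 | 1.85 | 0.04 |

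The estimates rise above 1.2 in the unequal rows because more of the worse subjects were placed in the placebo arm. That is common to both fits; the shift is what the covariate definition adds.

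**Hand check of the 20% / 0% rows.**

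- Placebo: Yes share = 0.5 + 0.5 × 0.2 = 0.60. Mean offset among Yes = (0.5 × (−1) + 0.1 × 3) / 0.6 = −0.333 for 3 points, and (−0.5 + 0.6) / 0.6 = 0.167 for 6 points.
- Elezanumab: Yes share 0.50, offset −1.
- Weights: 0.6 × 0.4 = 0.24 and 0.5 × 0.5 = 0.25.
- γ for 3 points = (0.24 × (−0.333) − 0.25) / 0.49 = −0.673; shift = −0.673 × (−0.10) = 0.07.
- γ for 6 points = (0.24 × 0.167 − 0.25) / 0.49 = −0.429; shift = −0.429 × (−0.10) = 0.04.

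**Cruder range.** Taking γ directly as 1 to 4 and the arm difference as 2 to 10 percentage points gives 1 × 0.02 = 0.02 to 4 × 0.10 = 0.40. The top needs both extremes at once: a 10-point arm difference is 6 of 60 subjects per arm. In the simulation γ stays small because most Yes subjects had EVT before randomisation. It would be larger for a factor with few early users, and the documents give no expected share for tPA.

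**The case against.** The strongest reply is that the SAP means status at randomisation. SAP 8.2 uses that phrase for the general MMRM, 8.3.3 calls the two terms stratification factors, and where 7.2 departs from the randomised definition (11 versus 12 hours) it says so. A form that holds prior and concomitant entries is only a data source. This probably describes the intent. It does not remove the problem: 7.2 is the specific derivation rule, it has no cut-off, and a general phrase that gives way to other instructions does not override it.

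Three stronger readings are tempting, and the documents do not support them.

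- A reader might infer that SAP 8.1 orders analysts to replace a correct randomised stratum with the form value. It covers only subjects randomised in a wrong stratum.
- A reader might infer that a sizeable group with a worse early course is moved. No rate or profile is given, and protocol 5.4 points the other way on numbers: "Eligibility according to NIHSS score must be confirmed at least 1 hour after completion of IV tPA and/or EVT". Planned reperfusion should therefore be finished before randomisation.
- A reader might infer that the protocol flatly contradicts itself. Section 4.1 mentions use before randomisation and is silent on later use; it does not say that only earlier use is allowed.

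This is also an exploratory study without formal tests. That lowers the stakes, but the posterior probability against 0.6 is still the headline result.

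**Conclusion.** The point holds as a gap of low magnitude in the covariate definition. Taken literally, SAP 7.2 lets treatment after randomisation set a factor that the analyses treat as baseline, and nothing else in the SAP clearly prevents it. How many subjects this touches cannot be known from the documents and is probably few.

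The treatment effect is biased only if later use depends on the assigned arm; otherwise the result is a mislabelled stratum with essentially no shift. With unequal use, the simulated shift of up to 0.07 is 0.07 / 0.6 = 12% of the threshold. The crude product reaches 0.40, or 67% of it, only with both assumed extremes combined. Every rate and coefficient behind these figures is an assumption, so they do not show that the primary result would be materially biased. The reason to act is that the remedy is almost free.

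**What to change.** In SAP 7.2, define tPA = Yes and EVT = Yes as treatment for the index stroke started before the randomisation transaction, and have 8.1 refer to that definition. Limiting the source to entries classed as prior would not work, for the reason in Step 2.

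This needs clock times. Protocol 5.4 asks for dates of medications, and the documents do not show that times of tPA or EVT are collected; dates alone cannot order events on the day of randomisation. If times are missing, use the IRT strata, corrected only for documented entry errors made before randomisation.

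Tabulate later tPA and EVT by arm as a post-randomisation event; Table 1 could state how it is handled. The synopsis, protocol 4.1 and protocol 5.4 should be reconciled on when use is permitted; which is right is for the sponsor.

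The cost is one or two SAP sentences, one small table and a protocol wording edit. The IRT route needs no new data. The change should be made before the interim lock at which the randomisation is loaded.
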